6.1 Study Interventions Administered

6.1.1 Investigational Products

Protocol Number: 20200439

Date: 05 June 2024 Page 55 of 176

Table 6-1. Investigational Products

	Table 0-1. Investigational Froducts	
	Amgen Investigational Product: ^a	Amgen Investigational Product: ^a
Study Treatment Name	Tarlatamab	AMG 404
Dosage Formulation	Tarlatamab is supplied as a sterile, single use, preservative free lyophilized drug product containing mg of tarlatamab per vial. Tarlatamab is intended for reconstitution with sterile water for injection and dilution in an intravenous (IV) bag with normal saline (% sodium chloride) and an IV solution stabilizer. The drug product is formulated with MM L-glutamic acid, % (w/v) sucrose, % (w/v) polysorbate 80, at a final pH of	Note: As of Protocol Amendment 3, AMG 404 will not be supplied. AMG 404 is supplied in a 3 mL Type 1 glass tubing vial containing 1 mL deliverable volume of mg/mL. The drug product is formulated with mM acetate (sodium counterion), (w/v) sucrose, 0.01% (w/v) polysorbate 80, pH and will be prepared for IV administration by dilution.
Unit Dose Strength(s)/ Dosage Level(s) and Dosage Frequency	The starting dose and dosing schedule of tarlatamab will be as the target dose with 1-step dosing. Tarlatamab will be administered after the target dose is reached. If the combination of tarlatamab and AMG 404 is not tolerated (based on target DLT rate > 30%), tarlatamab dose level will be further dose reduced or the day of administration of AMG 404 in combination with tarlatamab will be adjusted.	mg
Route of Administration	IV	IV
Accountability	The total volume of preparation, dose, start date/time, stop date/time, and lot number are to be recorded on each subject's CRF(s).	The total volume of preparation, dose, start date/time, stop date/time, and lot number are to be recorded on each subject's CRF(s).
Dosing Instructions	Tarlatamab will be administered as a short-term IV infusion for 60 minutes (± 10 minutes) followed by a flush once (except in cycle 1 where 1-step-dosing will be implemented).	AMG 404 will be delivered using infusion pumps approved for use by the appropriate regulatory authority for the country in which the subject is undergoing treatment. AMG 404 solution for infusion will be prepared in bags for IV infusion and delivered through infusion lines. The drug will be administered as a short-term IV infusion at a constant flow rate over 30 minutes

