6.2.1.4 Dose-limiting Toxicities

Dose-limiting toxicities are defined as any adverse event with an onset within first following first dose of tarlatamab with any of the following criteria unless clearly related to causes other than tarlatamab:

All grade 3 adverse events except

Protocol Number: 20200439

Date: 05 June 2024 Page 59 of 176

Fatigue lasting less than 7 days

- Grade 3 non-febrile neutropenia that improves to ≤ grade 1 within 3 weeks including the use of growth factor support per neutropenia management guidelines (see Section 6.8.5)
- Endocrinopathies, if manageable with replacement therapy
- Grade 3 nausea/vomiting or diarrhea for less than 72 hours with adequate antiemetic and other supportive care
- Grade 3 amylase or lipase values that are not associated with symptoms or clinical manifestations of pancreatitis
- Grade 3 hematologic lab abnormalities that are not considered clinically relevant
- Grade 3 electrolyte abnormality that lasts up to 72 hours, is not clinically complicated, and resolves spontaneously or responds to conventional medical interventions
- Grade 4 adverse event regardless of duration, except:
 - Grade 4 non febrile neutropenia lasting less than or equal to 7 days including the use of growth factor support per neutropenia management guidelines (see Section 6.8.5)
 - Grade 4 electrolyte abnormality that lasts up to 72 hours, is not clinically complicated, and resolves spontaneously or responds to conventional medical interventions
 - Grade 4 amylase or lipase values that are not associated with symptoms or clinical manifestations of pancreatitis
 - Grade 4 hematologic lab abnormalities that are considered not clinically relevant
- Grade 5 adverse events
- Recurrent grade 2 or higher pneumonitis
- Without exception, any other toxicity requiring permanent discontinuation of AMG 404 per Table 6-2.

The following adverse events will NOT be adjudicated as DLT regardless of the grade or duration:

- Lymphopenia
- Fever
- Tumor lysis syndrome including associated manifestations attributable to TLS (eg, electrolyte abnormalities, renal dysfunction, hyperuricemia)
- 6.2.2 Dosage Adjustments, Delays, Rules for Withholding or Restarting, Permanent Discontinuation

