	Grade 3 (increase of 7 or more stools per day over baseline; incontinence; hospitalization indicated; severe increase in ostomy output compared with baseline; limiting self-care ADL)	Withhold		
	Grade 4 (life-threatening consequences; urgent intervention indicated)	Permanently discontinue	· ,"	consider GI consultation and endoscopy to rule out colitis.

Footnotes defined on last page of this table

Page 1 of 6

Protocol Number: 20200439

Date: 05 June 2024 Page 64 of 176

Table 6-2. AMG 404 Dose Modification and Toxicity Management Guidelines for Immune-Related Adverse Events

Immune-Related Adverse Reactions	Severity or Specific Conditions	AMG 404 Dose Modification	Management with Corticosteroids and/or Other Therapies	Monitor & Follow-up	
Hepatotoxicity	When applicable, refer to Section 11.7 for managing AST and/or ALT and/or total bilirubin elevations, when other liver parameters remain within normal limits (eg, INR).			rameters remain	
Immune-mediated hepatitis ^a	Grade 1 (AST or ALT > ULN but < 3 x ULN) without elevated total bilirubin	Continue	Consider holding for concerning lab value trend.		
(Adapted from NCCN Guidelines)	Grade 2 (AST or ALT 3 to 5 x ULN) without elevated total bilirubin	Withhold	Consider corticosteroids at an initial dose of mg/kg/d prednisone (or equivalent) followed by taper.	Monitor with liver function tests more frequently until returned to baseline	
	Grade 3 (AST or ALT 5 to 20 x ULN) without elevated total bilirubin (Without a clear alternative etiology. If a clear alternative etiology, then withhold, do not discontinue AMG 404.)		Administer corticosteroids at an initial dose of mg/kg/d prednisone (or equivalent) followed by taper. Consider mycophenolate mofetil if refractory to corticosteroids or no improvement after 3 days.		
	Grade 4 (AST or ALT > 20 x ULN) without elevated total bilirubin (Without a clear alternative etiology. If a clear alternative etiology, then withhold, do not discontinue AMG 404.)	Permanently discontinue	Administer corticosteroids at an initial dose of mg/kg/d prednisone (or equivalent) followed by taper. Consider mycophenolate mofetil if refractory to corticosteroids or no improvement after 3 days.	or stable. Additional management per institutional and professional society guidelines.	

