DCR is defined as the incidence of a BOR of a confirmed response (CR/PR) or SD while on study as defined by modified RECIST 1.1.

Date: 27 Sep 2024 Page 23 of 51

Duration of Disease Control (DoDC)

The duration of disease control (in month) is defined as time from the earlier date of first dose of tarlatamab or AMG 404 to disease progression or death due to any cause, whichever occurs first. DoDC will be calculated only for subjects with a best overall response of CR, PR or SD.

Subjects will be censored following the censoring strategy described in the analyses of PFS (Appendix C).

Duration of Response (DOR)

The duration of response (in months) is defined as time from first evidence of CR or PR to disease progression or death due to any cause, whichever occurs first. DOR will be calculated only for subjects who achieve a best overall response of PR or CR.

DOR (Months)= (PD / death date - response start date + 1) ×12 / 365.25

Subjects will be censored following the censoring strategy described in the analyses of PFS (Appendix C).

Dose Limiting Toxicity (DLT)

Dose-limiting toxicity (DLT) is defined as tarlatamab-related toxicity with an onset within the first following first dose with the criteria defined in section 6.2.1.4 of the Protocol.

End of Follow-Up

It is defined as when the last subject completes the last protocol-specified assessment in the study.

End of IP administration

End of IP Admin for each subject is defined as the date the decision was made to end IP as recorded on the End of Investigational Product Administration CRF page.

End of Study (Individual Subject)

End of study for each subject is defined as the date when the subject completed protocol-specified last visit shown in the schedule of activities. The date will be recorded on the End of Study CRF page.

Date: 27 Sep 2024 Page 24 of 51

End of Study (End of Trial)

It is defined as the date when the last subject across all sites is assessed or receives an intervention for evaluation in the study (i.e., last subject last visit), including any additional part in the study (eg, long-term follow-up, as applicable.

End of Treatment (EOT)

It is defined as the last assessment per the protocol-specified treatment phase of the study (i.e., end of last treatment cycle) for an individual subject. For subjects who prematurely discontinue investigational product treatment, the EOT should occur as soon as possible (within after a state of investigational product was administered.

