Events categorized as Adverse Events (AEs) starting on or after first dose of tarlatamab or AMG 404 as determined by "Did event start before first dose of investigational product" equal to "No" or missing on the Events eCRF and up to and including after the last dose of tarlatamab or AMG 404 or the End of Study date, whichever is earlier. Events that are directly related to lung cancer or disease progression (including, but not limited to, preferred terms "Small cell lung cancer", "Disease progression" etc.) will be excluded from TEAE analysis.

The severity of each adverse event will be graded using the CTCAE version 4.0 with the exceptions - CRS will be graded according to American Society for Transplantation and Cellular Therapy (ASTCT) (Lee et al, 2019). Adverse events will be coded using latest version of MedDRA.

Treatment-Emergent Adverse Event (TEAE) For Extended Period

An adverse event that occurs after the since the last dose of tarlatamab or AMG 404 and up to after last dose of tarlatamab or AMG 404 or the End of Study date, whichever occurs later. The severity of each adverse event will be graded using the CTCAE version 4.0. Adverse events will be coded using latest version of MedDRA.

Treatment-Related AE

A treatment-related AE is any treatment-emergent AE with the relationship flag on the Events eCRF indicating there is a reasonable possibility that the event may have been caused by tarlatamab or AMG 404. Event with missing relationship with protocoldefined treatment regimen in each cohort will be assumed to be treatment-related.

6. Analysis Sets

The following sub-sections describe the analysis sets to be used.

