7.1 Interim Analysis and Early Stopping Guidelines

Safety data will be reviewed on an ongoing basis.

During dose exploration (Part 1) and formally during dose level review meetings (DLRMs), Amgen, in consultation with the site investigators, will review all available cumulative data by cohort prior to making dose escalation or dose de-escalation recommendation. Adverse events and DLTs observed in all subjects will be evaluated continually and fully integrated into all DLRMs and considered in all enrolment and dosing decisions.

During dose expansion (Part 2), Amgen will conduct evaluations of the ongoing grade 4 or higher treatment-related TEAEs to assess if the threshold for possible early trial termination has been reached. The safety interim will occur for every subjects

Date: 27 Sep 2024 Page 30 of 51

enrolled who have had opportunity to have at least of follow up since the first dose of tarlatamab. If this threshold is met, enrollment to dose expansion will be halted pending review of safety data by the DLRT. After receiving the DLRT recommendation, Amgen will choose to take one of the following actions.

- Terminate the trial
- Amend the protocol to potentially improve the benefit/risk for subjects (eg, increase safety monitoring, modify dose/schedule, mandate premedication)
- Continue dose expansion without any changes.

The stopping rules use a Bayesian approach proposed by Thall (Thall et al, 1995) to terminate the study if the posterior probability that the grade 4 or higher treatment related TEAE rate is greater than 20% is > 80%. The stopping boundaries assume a prior distribution of Beta (0.40, 1.60) are presented in **Table 4** and the operating characteristics with pre-specified batch size of new subjects per batch are presented in **Table 5**.

Table 4. Stopping Boundary for Dose Expansion with Posterior Probability of 80% and Grade 4 or Higher Treatment-related Adverse Event Limit of 20%

Number of Subject	Stop Subjects if Observing This Many Grade 4 or Higher Treatment-related Adverse Events
	≥ 4
	≥ 6
	≥ 9
	Dose Expansion Complete

 Table 5. Operating Characteristics with Batch Size of
 Subjects

True Grade 4 or Higher	Probability of Early	Average Dose Expansion
Treatment-related	Stopping of Dose	Sample Size
Adverse Event Rate	Expansion	-
0.10	2.0%	39.5
0.15	9.7%	37.6
0.20	25.8%	33.9
0.25	47.7%	28.8
0.30	69.2%	23.4

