9.6 Safety Analyses

9.6.1 Analyses of Dose Limiting Toxicities

The subject incidence of DLT will be tabulated by planned dose level. The analysis of DLTs will be conducted on DLT analysis set. The subject incidence of DLTs will be used to estimate final DLT rates for each dose level using isotonic regression (Ji et al, 2010). Refer the Section 3.3 of adaptive design for more details.

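### SAP Section 5 counts only tarlatamab-related toxicities as DLTs, while protocol 6.2.1.4 counts every qualifying event unless a cause other than tarlatamab is clear

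*SAP*

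**What the plan says.** Protocol Section 6.2.1.4 opens with one sentence that stands over all its criteria. Any adverse event with onset in the DLT window that meets a listed criterion is a DLT "unless clearly related to causes other than tarlatamab". The criteria include all grade 3 events outside a list of exceptions, grade 4 events with a shorter list, grade 5 events and recurrent pneumonitis of grade 2 or higher. The last criterion is "Without exception, any other toxicity requiring permanent discontinuation of AMG 404 per Table 6-2".

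SAP Section 5 (Definitions) reads "Dose-limiting toxicity (DLT) is defined as tarlatamab-related toxicity" and takes the criteria from protocol 6.2.1.4 by reference. AMG 404 does not appear in its attribution test.

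The counts are then used in SAP Section 9.6.1: "The subject incidence of DLTs will be used to estimate final DLT rates for each dose level using isotonic regression". SAP Section 3.3 selects the level whose estimate lies nearest 30%. SAP Section 10 states that nothing departs from the analyses in the protocol.

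**The concern.** DLT is a primary endpoint of a trial that tests a combination, and the two documents put the burden of attribution on opposite sides. Under the protocol, doubt about the cause keeps an event in. Under the SAP, doubt leaves it out unless someone has called it tarlatamab-related. The SAP filter can remove events and cannot add any.

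The filter could be applied in practice. The sample serious adverse event form (protocol Figure 11-1) asks for the relationship to each drug separately, so a program could select on the tarlatamab answer alone. The same SAP section also has a definition that covers both drugs: an adverse event is treatment-related when "there is a reasonable possibility that the event may have been caused by tarlatamab or AMG 404". A programmer reading Section 5 would take the narrower wording for DLTs as deliberate. Because Section 10 declares no change, a reader of the study report would not know that the DLT table might rest on a different rule from the one the protocol sets.

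**Working it through.** **Step 1. The two rules side by side.** Take an event in the DLT window that meets a 6.2.1.4 criterion.

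| Attribution of the event | Protocol 6.2.1.4 | SAP Section 5, read literally |
|---|---|---|
| Tarlatamab-related | DLT | DLT |
| Cause unclear, not called tarlatamab-related | DLT | Not a DLT |
| Attributed to AMG 404, not clearly unrelated to tarlatamab, not called tarlatamab-related | DLT | Not a DLT |
| Clearly due to AMG 404 alone, meets a grade-based criterion | Not a DLT (lead-in) | Not a DLT |
| Clearly due to AMG 404 alone, meets only the AMG 404 discontinuation criterion | Ambiguous | Not a DLT |
| Clearly due to some other cause, such as the tumor | Not a DLT on the lead-in | Not a DLT |

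The documents differ in rows 2 and 3 however the protocol is read. Row 5 depends on a protocol ambiguity taken up under the objection.

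**Step 2. An example.** Protocol Table 6-2 stops AMG 404 permanently for grade 2 myocarditis. Grade 2 meets none of the grade 3, 4 or 5 criteria, and the only other grade 2 criterion concerns pneumonitis. The event is therefore a DLT only through the AMG 404 discontinuation criterion. If the investigator suspects AMG 404 and cannot exclude tarlatamab, the protocol counts it. SAP Section 5 does not, unless it is also called tarlatamab-related.

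**Step 3. Direction.** Every event that passes the SAP test also passes the protocol test, since a tarlatamab-related event is not clearly due to something else. So the SAP count is at most the protocol count at each dose level.

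**Step 4. Can one event matter?** This is an illustration; the cohort sizes are redacted.

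- Inputs: Beta(1,1) prior, target 30%, equivalence interval 25% to 33%, 95% overdose cut (protocol 4.1). With these, mTPI-2 reproduces all seven blocks of protocol Table 4-2 at inferred sizes 3, 4, 5, 6, 7 (or 8), 9 and 10 (or 11).
- Assume two levels of 6 subjects, with protocol counts of 1/6 and 3/6. For 3/6 the posterior probability that the DLT rate exceeds 30% is 0.874, below 0.95. The upper level is de-escalate but not unacceptably toxic, so it stays selectable.
- The rates already rise with dose, so isotonic regression returns them: 16.7% and 50.0%. Distances to 30% are 13.3 and 20.0 points, and the lower level is picked.
- Drop one event at the upper level: 1/6 and 2/6 give 16.7% and 33.3%. Distances are 13.3 and 3.3 points, and the upper level is picked.

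**Step 5. How often?** The documents give no rate for events on which the two rules disagree. If a share q of subjects has one, the chance that a level of n subjects loses at least one DLT is 1 − (1 − q)^n. Both q and n are assumed here.

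| q (assumed) | n = 6 | n = 10 |
|---|---|---|
| 1% | 1 − 0.99^6 = 5.9% | 1 − 0.99^10 = 9.6% |
| 5% | 1 − 0.95^6 = 26.5% | 1 − 0.95^10 = 40.1% |

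These figures show sensitivity only. They do not estimate what happened in the trial.

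**The case against.** **The SAP keeps all the criteria.** It imports 6.2.1.4 by reference, including the AMG 404 criterion. That is true. Only the attribution test differs, and the point is confined to that.

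**A reader might infer that the protocol makes every toxicity that stops AMG 404 a DLT, whatever its cause, and that the SAP contradicts this.** The words at the start of "Without exception, any other toxicity requiring permanent discontinuation of AMG 404 per Table 6-2" invite that reading. But the lead-in stands over every criterion, and those words may mean only that this criterion, unlike the grade 3 and grade 4 ones, carries no list of exceptions. An event clearly due to AMG 404 alone is therefore ambiguous within the protocol.

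**A reader might take raised transaminases as the natural example,** from the Table 6-2 row "Grade 3 (AST or ALT 5 to 20 x ULN) without elevated total bilirubin (Without a clear alternative etiology". It does not fit the AMG 404 criterion. Grade 3 AST or ALT is already covered by the general grade 3 criterion and is not among its exceptions, whereas the last criterion is for other toxicities. The lead-in applies to it in the ordinary way.

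**Tarlatamab attribution may be intended.** Part 1 varies tarlatamab and holds AMG 404 fixed. The Part 2 stopping rule, which covers both drugs, monitors a different endpoint. This explains why both documents anchor on tarlatamab, and the wider Part 2 definition proves no inconsistency. It does not explain why the SAP reverses the default for doubtful cases.

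**The decisions are past.** Enrollment ended in January 2023, Part 2 followed completion of Part 1, and the SAP is dated 27 September 2024. The protocol also lets the recommended phase 2 dose rest on emerging safety, efficacy and pharmacodynamic data before an MTD is reached. All of this stands, and it limits the point to the reported DLT table and estimates.

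**Conclusion.** The point holds as a mismatch of definitions. SAP Section 5 is narrower than protocol 6.2.1.4 for events of unclear cause, and for events attributed to AMG 404 but not clearly unrelated to tarlatamab. The change is not declared.

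The direction is certain: reported DLT counts can only match or fall below the protocol's. The size is unknown from the documents and may be zero. Any effect requires that such an event occurred in Part 1 and that the DLT table is programmed from SAP Section 5. If the table instead uses the calls made at the DLRMs, the numbers are right and only the SAP text is wrong.

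A reader might infer from the change of pick in the working that a wrong dose was chosen. The documents do not support that. The counts and level sizes there are assumed, and dosing recommendations were made at the DLRMs, not from the SAP.

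**What to change.** In SAP Section 5, replace the tarlatamab-related test with the protocol's own attribution wording: any adverse event in the window that meets a 6.2.1.4 criterion, "unless clearly related to causes other than tarlatamab". Add one sentence stating that the DLT analysis uses the DLT calls made at the DLRMs, without re-scoring.

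The sponsor should also state how the DLRMs treated an event that met the AMG 404 discontinuation criterion and was clearly due to AMG 404 alone. The SAP should record that practice. It should not settle the protocol's ambiguity with new wording, for example by adding that such events count whichever drug caused them.

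The cost is one replaced phrase and two sentences, with no new data and no protocol change. A listing of Part 1 subjects who stopped AMG 404 permanently for toxicity in the DLT window, with the relationship to each drug and the DLT call, would let a reader check the count, but it is optional.

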6.1 Full Analysis Set

Not applicable for this study.

6.2 Safety Analysis Set

The Safety Analysis Set will consist of all subjects who received at least 1 dose of any Investigational Products (tarlatamab/AMG 404). The analysis of all safety endpoints, unless noted otherwise, will be conducted on the Safety Analysis Set.

Date: 27 Sep 2024 Page 29 of 51

6.3 DLT Analysis Set

For the dose exploration part of the study, the analysis of DLT will be conducted on the DLT Analysis Set, defined as all subjects that are enrolled and received at least 1 dose of tarlatamab or AMG 404 with an evaluable DLT endpoint. The DLT endpoint is evaluable if either: 1) the subject experiences a DLT, or 2) the subject does not experience a DLT and receives tarlatamab or AMG 404 treatment as planned in cycle 1 and has been followed for safety events a minimum of from date of first dose administration of tarlatamab or AMG 404.

6.4 Pharmacokinetic Analyses Set(s)

The PK Analysis Set will contain all subjects who have received at least 1 dose of the Investigational Product and have at least 1 PK sample collected. These subjects will be evaluated for PK analysis unless the number of data points required for analysis is not enough, or significant protocol deviations have affected the data, or if key dosing or sampling information is missing.

